#### In-vitro Animal Testing

Safety was evaluated in an over-insertion mode (contrary to the Instructions for use) in an *in-vitro* animal model. For normal operation, a depth control collar limits the insertion of the Clearing Stem into the EAD; thus prevents the Clearing Stem tip from exiting the EAD. To test safety, *ex-vivo* porcine stomach and small intestine tissue samples with thicknesses similar to humans of age 0 to 39 years of age were examined in the simulated over-insertion mode. A porcine model was selected due to similarity of gastric features to that of humans aged 0 to 39 years. The range of intestinal thickness (jejunum) for human ages 0 to 39 years is 0.6 – 1.0 mm (**Table 3**). Tissue samples from the porcine intestine tissue used for testing were between 0.284 mm and 1.0 mm as measured via two independent methodologies.

As such, it was concluded that the tissue samples used for this safety testing were representative of both adult and pediatric patients and the results of the testing are applicable to both populations (**TR-4010-022**).

The EAD(A) Clearing Stem was advanced at a rate of 65-70 mm/min to simulate actual use. The maximum force of the Clearing Stem tip on the tissue sample was 3.597 N. The advancement of the Clearing Stem stopped when the wire was observed to be bent at approximately 45°. In the 60 trials run, the Clearing Stem caused small indentations, but no full puncture was observed (**TP-4010-008**, and **TR-4010-008**).

This testing was repeated for the EAD(P) Clearing Stem design. Tissue samples from the porcine intestine (jejunum) tissue were on average between 0.62 mm and 0.92 mm. It was concluded through statistical analysis that this was representative of both adult and pediatric patients and the results of the testing are applicable to both populations. No punctures of porcine intestine (jejunum) tissue samples were achieved in a realistic worst-case misuse test scenario (**TP-4021-020** and **TR-4021-020**).

#### In-vivo Animal Testing

The safety and efficacy of the Alpha (first design iteration) EAD(P) TubeClear® Clearing Stem design was tested in a live porcine model at the Medical University of South Carolina. Use of TubeClear® was performed in a porcine model to simulate pediatric insertion by [name], VMD, a veterinarian, [name], FACG, CNSP, AGAF, FASGE, a gastroenterologist, conducted the standard Intervention and [name], DVM, Ph.D., a board certified pathologist, conducted the pathology evaluations.

1) The efficacy of the EAD(P) Clearing Stem in clearing EAD(P)s with simulated occlusions was evaluated in a porcine model. Patency was restored in an average time of 2.37 minutes (**TP-5017-009**, **TR-5017-009** and **TR-5017-010**).

2) Safety was evaluated in an over-insertion mode (contrary to the Instructions for use). For normal operation, a depth control collar limits the insertion of the Clearing Stem into the EAD; thus prevents the Clearing Stem tip from exiting the EAD. To test safety, the collar was removed, and the Clearing Stem's distal tip was intentionally advanced approximately 2.5cm beyond the distal end of the EAD(P) so that the distal tip contacted and remained in contact with the porcine mucosal intestinal tissue for six (6) minutes while in 'on mode' (**TP-4010-008**, and **TR-4010-008**). No evidence suggested TubeClear® (consistent to instructions for use) produced intestinal trauma beyond that which can be caused by insertion of an EAD(P). In the over-insertion situation (inconsistent to instructions for use), the Clearing Stem caused lesions that were highly localized, but no full puncture was observed.

### **1.3.2 Clinical Studies**

#### Human Pharmacokinetics

TubeClear® is a medical device. Therefore, human pharmacokinetics is not applicable.

#### Clinical Data from Field Use in Adults (including post-marketing surveillance data)

To date, one patient has been enrolled in an IRB approved TubeClear® clinical Study. The Study was at Walter Reed National Military Medical Center, but was terminated after the PI retired from the armed forces. TubeClear® restored patency, and there was no report of discomfort during use (**Appendix E**).

Once TubeClear® was FDA cleared for commercial use, several hospitals conducted post-marketing evaluations. Wexner Medical Center at the Ohio State University evaluated the device and completed evaluation questionnaires (**Appendix E**). Three other facilities have used TubeClear® and provided results (**Appendix E**). All seventeen (17) TubeClear®

applications in adults were successful in restoring patency. No adverse events or pain/discomfort in patients were reported.

TubeClear® undergoes an annual Post-Market Surveillance study. No adverse events or other significant issues have been reported by end users thus far. Moreover, FDA maintains an adverse event database known as MAUDE (Manufacturer and User Facility Device Experience), where end users report adverse events for medical devices for public disclosure. No adverse events have been reported to MAUDE for TubeClear® since original market clearance in 2012.

#### Clinical Studies in Children

To date, there have been no IRB-approved pediatric clinical studies.

A single male pediatric off-label use of TubeClear® has been reported for compassionate care in a 14 Fr NG EAD. This pediatric use was successful without any adverse event or patient discomfort.

#### **1.4 Selection of Drugs and Dosages**

TubeClear® is a medical device. Therefore, selection of drugs and doses is not applicable.

#### **1.5 Relevant Literature and Data**

The established age-appropriate pain scales used in this study have been validated and cited extensively.

#### **1.6 Compliance Statement**

This Study will be conducted in full accordance with all applicable Children's Hospital of Philadelphia (CHOP) Research Policies and Procedures and all applicable Federal and State laws and regulations including 45 CFR 46, 21 CFR Parts 50, 54, 56, 312, 314 and 812 and Good Clinical Practice. All episodes of noncompliance will be documented.

The investigators will conduct the Study in accordance with this protocol, obtain informed consent and, where applicable, assent, and will report unanticipated problems involving risks to Subjects or others in accordance with the CHOP IRB Policies and Procedures and all Federal requirements. Collection, recording, and reporting of data will be accurate and will ensure the privacy, health, and welfare of research Subjects during and following Study completion.

## 2 STUDY OBJECTIVES

The objectives of this study are to 1) evaluate feasibility and tolerability of TubeClear® to restore patency in occluded EAD(P)s, and 2) compare efficacy of TubeClear® to the CHOP Standard Treatment to restore patency in occluded EAD(P)s. This study will be carried out in phases – Phase I followed by Phase IIA and IIB to run concurrently. The objective of Phase I is to evaluate feasibility and tolerability of TubeClear® intervention to restore patency in occluded EAD(P)s in patients who have not attained their 18th birthday. The objective of Phase IIA is to measure the ability of TubeClear® intervention to restore patency in occluded EAD(P)s in a younger age group i.e. patients who have not attained their 11th birthday. The objective of Phase IIB is to compare efficacy of TubeClear® intervention with the CHOP Standard Treatment to restore patency in occluded EAD(P)s in patients who are between 11 years of age and have not attained their 18th birthday using a randomized controlled design.

For the purpose of this Study, EAD(P)s are ND, NG, and NJ 6 – 8 Fr, 38 – 140 cm; NG tube (Corflo, Corpak MedSystems) used as a J tube inserted through a G tube, 6 – 8 Fr, 38 – 140 cm; and AMT GJ tube, 14 Fr, 38 – 140 cm (15 – 55 in). In all phases, if the study intervention is unable to restore EAD(P) patency, further steps to restore patency will be carried out by the clinical team per usual practice.

### 2.1 Primary Objective (or Aim)

The primary objectives of this study are to 1) evaluate feasibility and tolerability of TubeClear® to restore patency in occluded EAD(P)s, and 2) compare efficacy of TubeClear® to the CHOP Standard Treatment to restore patency in occluded EAD(P)s.

The primary endpoints in Phase I are feasibility and tolerability of TubeClear® intervention. Feasibility will be defined as ability of the user to operate TubeClear® device (as per instructions and training in **Appendix F**) from insertion of the clearing stem into the occluded EAD(P) through device activation to patency restoration. Tolerability will be defined as ability of the Subject to undergo TubeClear® intervention.

The primary endpoint in Phase IIA is the ability of TubeClear® intervention to restore patency in Subjects with occluded EAD(P)s. This will be termed as EAD(P) patency restoration and will be measured by the ability to flush the EAD(P) with 10 ml of air within five (5) minutes after completion of the intervention.

The primary endpoint of Phase IIB is the efficacy of TubeClear® intervention compared to CHOP Standard Treatment to restore patency in Subjects with occluded EAD(P)s. EAD(P) patency restoration will be measured by the ability to flush the EAD(P) with 10 ml of air within five (5) minutes after completion of either intervention.

### 2.2 Secondary Objectives (or Aim)

The secondary objectives of this study are to assess subject pain, changes in physiological parameters, distress related EAD(P) events and adverse events related to the interventions.

In Phase I, Subject pain will be assessed before and after use of TubeClear® intervention using established age-appropriate pain scales. Acute changes in physiologic parameters will be measured, including changes in heart rate, blood pressure and respiratory rate. Distress related EAD(P) events which may be manifested by pulling or yanking of the EAD(P) will be monitored in relation to intervention. Following the TubeClear® intervention, each Subject will receive an abdominal radiograph with contrast. Radiographs will be reviewed by a radiologist (blinded to the study) for EAD(P) adverse events (i.e., EAD(P) displacement, EAD(P) damage, enteral tract tissue injury) attributable to the TubeClear® intervention.

In Phase IIA, Subject pain will be assessed before and after use of TubeClear® intervention using established age-appropriate pain scales. Acute changes in physiologic parameters will be measured, including changes in heart rate, blood pressure and respiratory rate. Distress related EAD(P) events which may be manifested by pulling or yanking of the EAD(P) will be monitored in relation to intervention. Following the TubeClear® intervention, each Subject will receive an abdominal radiograph with contrast. Radiographs will be reviewed by a radiologist (blinded to the study) for EAD(P) adverse events (i.e., EAD(P) displacement, EAD(P) damage, enteral tract tissue injury) attributable to the TubeClear® intervention.

In Phase IIB, Subject pain will be assessed before and after use of either intervention using established age-appropriate pain scales. Acute changes in physiologic parameters will be measured, including changes in heart rate, blood pressure and respiratory rate. Distress related EAD(P) events which may be manifested by pulling or yanking of the EAD(P) will be monitored in relation to either intervention. Following either intervention, each Subject will receive an abdominal radiograph with contrast. Radiographs will be reviewed by a radiologist (blinded to the study) for EAD(P) adverse events (i.e., EAD(P) displacement, EAD(P) damage, enteral tract tissue injury) attributable to either intervention. Incidence of adverse events attributable to the intervention (i.e. EAD displacement, EAD damage, enteral tract tissue injury) following the intervention will be monitored and reported in both groups.

In all phases, surveillance will include daily assessment for adverse events related to the respective study intervention (i.e. subject pain, feeding intolerance, EAD(P) displacement, EAD(P) damage, enteral tract tissue injury) and will continue for three (3) days. Patients who are discharged from the hospital prior to 3 days will be followed up daily by phone until completion of 3 days following study interventions.

### **3 INVESTIGATIONAL PLAN**

#### **3.1 General Schema of Study Design**

This Study will be carried out in phases in the CHOP Pediatric Intensive Care Unit (PICU), Progressive Care Unit (PCU), and/or Interventional Radiology Department (IR). Phase I will study the feasibility and tolerability of TubeClear® intervention to restore EAD(P) patency in consecutive eligible Subjects (n=15) with occluded EAD(P)s who have not attained their 18th birthday.

After completion of Phase I, a detailed summary of the 15 enrolled subjects will be submitted to the IRB for review of protocol compliance/feasibility, incidence of Adverse Events (if any), and subject pain/tolerability. Following successful completion of Phase I as deemed by the IRB, the Study will proceed to Phase IIA and IIB to run concurrently.

Phase IIA will measure the ability of TubeClear® intervention to restore patency in consecutive eligible Subjects (n=15) with occluded EAD(P)s who have not attained their 11th birthday.

Phase IIB will consist of a randomized efficacy comparison between TubeClear® intervention (experimental, n=17) and CHOP Standard Treatment (control, n=17) in eligible Subjects with occluded EAD(P)s who are between 11 years of age and have not attained their 18th birthday. The overall Study Design is summarized in the Study Flow Chart (**Figure 1**).

##### **3.1.1 Screening Phase**

In Phase I, potential Subjects are pediatric patients who have not attained their 18th birthday, and are admitted to the CHOP PICU, PCU, or IR with an existing or a newly inserted EAD(P) that becomes occluded.

In Phase IIA, potential Subjects are pediatric patients who have not attained their 11th birthday, and are admitted to the CHOP PICU, PCU, or IR with an existing or a newly inserted EAD(P) that becomes occluded.

In Phase IIB, potential Subjects are pediatric patients who are between 11 years of age and have not attained their 18th birthday, and are admitted to the CHOP PICU, PCU, or IR with an existing or a newly inserted EAD(P) that becomes occluded.

Patients will become eligible once an occlusion in the EAD(P) is reported and they meet all inclusion/exclusion criteria for the Study. An occlusion is defined by direct identification of a clog or through a feeding pump alarm that sounds when patency of an EAD(P) is disrupted. Potential eligible Subjects will be identified by screening the electronic health records (EHR). In addition, CHOP staff may notify the research personnel when there is a potential Subject. Eligible subjects will be approached for informed consent and, when applicable, assent to participate in the study. If ineligible, research personnel will document patient information to prevent further consideration. Eligible subjects may be enrolled more than once and up to a maximum of three times in the study for each instance of EAD(P) occlusion.

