## **3.2 Allocation to Treatment Groups and Blinding**

All Subjects in Phase I and Phase IIA of the Study will receive TubeClear® to restore patency of the occluded EAD(P).

All Subjects in Phase IIB will be randomized into the TubeClear® intervention (experimental) or CHOP Standard Treatment (control) group according to a predetermined computer generated randomization sequence. The randomization sequence will be kept in individual opaque sealed envelopes to be opened after the Subject is consented and enrolled in Phase IIB. To ensure an appropriate balance of participation in both the experimental and control groups, balanced, permuted block randomization will be used, as Phase IIB is not blinded.

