#### **3.3.2 Total Number of Study Sites/Total Number of Subjects Projected**

The Study will be conducted at one site, the Children's Hospital of Philadelphia (CHOP) in the Pediatric Intensive Care Unit (PICU), Progressive Care Unit (PCU), and Interventional Radiology Department (IR). A total of 64 Subjects will be enrolled in this Study – 15 in Phase I and 49 in Phase II.

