### 6.3.3 Primary Objective Analysis

Data from Phase I and Phase IIA will be observational and will not test a hypothesis. Data on feasibility and tolerability from Phase I and data on EAD(P) patency restoration will be reported as counts and percentages.

In Phase IIB, the primary objective is efficacy comparison between TubeClear® intervention and CHOP Standard Treatment. EAD(P) patency restoration will be measured by the ability to flush the EAD(P) with 10 ml of air within five (5) minutes following the Intervention. Efficacy is the proportion of EAD(P)s restored to patency in each group. A chi-square analysis (or Fisher's exact test) will be performed to compare the efficacy of TubeClear® intervention to the CHOP Standard Treatment. Intention-to-treat analysis will be used to compare the efficacy of the TubeClear® intervention to the CHOP Standard Treatment. Patients will be analyzed according to their randomized allocation. Full reporting of any deviations from random allocation and missing responses will be recorded and assessed in accordance with the CONSORT guidelines. Exploratory-per-protocol analysis will also be reported.

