#### **6.3.4 Secondary Objective Analysis**

Data from Phase I and Phase IIA will be observational and will not test a hypothesis. Data on 1) pain, using established age-appropriate pain scales, 2) physiologic changes in vital signs, 3) distress related EAD(P) events, and 4) adverse events related to TubeClear® use will be described and reported as counts and percentages.

In Phase IIB, the secondary objectives between TubeClear® intervention and CHOP Standard Treatment include comparison of 1) time to intervention, 2) pain using established age-appropriate pain scales, 3) physiologic changes in vital signs, 4) distress related EAD(P) events, and 5) adverse events related to either group.

1. A log-rank test will be performed to compare intervention time of TubeClear® intervention to the CHOP Standard Treatment.
2. A Wilcoxon rank sum test will be performed to compare differences in subject pain and discomfort between TubeClear® intervention and CHOP Standard Treatment.
3. A t-test will be performed if the distributions are normal (or non-parametric equivalent, if the distributions are not normal) to compare differences in physiologic changes (i.e. vital sign changes) between TubeClear® intervention and CHOP Standard Treatment.
4. A Wilcoxon rank sum test will be performed to compare differences in distress related EAD(P) events (i.e. subject behavior such as pulling/yanking) between TubeClear® intervention and CHOP Standard Treatment.
5. A chi-square analysis (or Fisher's exact test) will be performed to compare the proportions of adverse events (i.e., EAD(P) displacement from the intervention; EAD(P) damage from the intervention; any enteral tract tissue perforation from the intervention) in TubeClear® intervention and CHOP Standard Treatment.

Intention-to-treat analysis will be used to compare the secondary endpoints between the TubeClear® intervention and the CHOP Standard Treatment. Patients will be analyzed according to their randomized allocation. Full reporting of any deviations from random allocation and missing responses will be recorded and assessed in accordance with the CONSORT guidelines. Exploratory-per-protocol analysis will also be reported.

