**Figure 9: Sample size as a function of power at three different alpha levels**

To ensure proper power is achieved a sample size of 17 Subjects in each group is needed (**Figure 9**).

- The efficiency of TubeClear® (Intervention time of TubeClear® to the CHOP Standard Treatment) is expected to be at least one standard deviation (40 minute difference of average time, 0.243 minute standard deviationxiii) greater than that of CHOP Standard Treatment based on bench testing.xiv Therefore, a sample size of 17 in each group is more than sufficient to show statistical significance of the desired effect.

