## **9 STUDY ADMINISTRATION**

### **9.1 Treatment Assignment Methods**

#### **9.1.1 Randomization**

A randomization sequence will be generated by computer program by the Study Sponsor for the randomized efficacy comparison in Phase IIB. The Study Team will be responsible for maintenance and execution of randomization sequence. The randomization sequence will be kept in individual sealed envelopes to be opened after the Subject is consented and enrolled in the Study. To ensure an appropriate balance of participation in both the TubeClear® intervention and CHOP Standard Treatment Groups, balanced, permuted block randomization will be used, as the Study is not entirely blinded.

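### Does allowing a child to be enrolled up to three times undermine the Phase IIB comparison, given that no rule covers a returning child?

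*Combined protocol and SAP*

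**What the plan says.** The Abstract (Study Interventions and Measures) and section 3.1.1 both provide for repeat enrolment: "Eligible subjects may be enrolled more than once and up to a maximum of three times in the study". The sentence goes on to tie each enrolment to an episode of tube occlusion.

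For Phase IIB, section 3.2 has the allocation envelope "to be opened after the Subject is consented and enrolled in Phase IIB". Section 9.1.1 says almost the same: "to be opened after the Subject is consented and enrolled in the Study". Neither mentions a child who comes back.

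Section 6.3.3 defines the primary outcome at tube level: "Efficacy is the proportion of EAD(P)s restored to patency in each group". It compares the arms by chi-square or Fisher's exact test and specifies intention-to-treat: "Patients will be analyzed according to their randomized allocation". Section 6.3.4 carries this over to the other outcomes: "Intention-to-treat analysis will be used to compare the secondary endpoints".

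The planned numbers are given in subjects. Section 3.3.2 says "A total of 64 Subjects will be enrolled in this Study", and section 6.4 says "a sample size of 17 Subjects in each group is needed", based on expected success of 95% with TubeClear and 50% with standard treatment.

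**The concern.** Three things are left unsaid: whether 17 per arm counts children or enrolments, whether a returning child is randomised again, and which of a child's occlusions enter the primary test. Section 6.3.3 also uses two units in one paragraph, tubes for the outcome and patients for the allocation.

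Each gap could matter. Chi-square and Fisher tests treat observations as independent, so several correlated results from one child in the same arm would make the p-value too small. If returning children are randomised again, a child may hold both allocations and has no obvious place in a patient-level intention-to-treat analysis. If only one occlusion per child is kept, repeat enrolments use up places among the 34, and the sample size has little slack. The comparison is also unblinded to the investigators (section 9.1.2), so a choice left open could be made with the results in view.

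**Working it through.** **Inputs.** From section 6.4: success 95% and 50%, alpha 0.05, 17 per arm. Assumed, because the documents give none of them: within-child correlation 0.1 to 0.5, the repeat patterns below, and a null success rate of (95% + 50%)/2 = 72.5%. Chi-square is taken without continuity correction, and both tests are two-sided.

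**1. The planned sample size.** Exact power = sum over (a, b) of Bin(a; n, 0.95) × Bin(b; n, 0.50) × 1[p(a, b) ≤ 0.05].

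| Children per arm | Fisher | Chi-square |
|---|---|---|
| 17 | 81.3% | 89.4% |
| 16 | 77.7% | 89.6% |
| 14 | 71.2% | 83.7% |

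Seventeen is the smallest number per arm that gives Fisher's test 80% power, so the plan's figure is reproduced for 17 independent observations per arm.

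**2. What the text supports.** Enrolment is tied to an occlusion (3.1.1), an envelope is opened after enrolment (3.2, 9.1.1), and the outcome is a proportion of tubes (6.3.3). Together these give one enrolment, one envelope and one result. The word subjects in 3.3.2 and 6.4 leans towards children as the count, but section 3.1.1 uses the same word for people who may be enrolled several times.

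**3. Type I error under that reading.** If treatment has no effect, allocation labels shuffled over 34 enrolments are unrelated to the outcomes, however correlated those are within a child. The number of successes in one arm then has the hypergeometric distribution on which Fisher's test rests. Simulation with 17 of 34 enrolments drawn at random per arm (block size is not stated) agrees:

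- Null 72.5%, with 32, 28, 18 or 12 distinct children behind the 34 enrolments: Fisher 1.8 to 2.1%, chi-square 4.4 to 4.7%.
- Null 50%: about 2.4% and 5.7%, against 2.4% and 5.8% with no repeats. The small chi-square excess comes from the test at this sample size, not from repeats.

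**4. Power under that reading.** With all occlusions analysed in the arm drawn and 95% versus 50%, power is about 81% (Fisher) and 89% (chi-square), as in step 1.

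**5. If a returning child kept its first arm** and all enrolments were counted (null 72.5%, correlation 0.1 to 0.5):

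| Children behind 17 enrolments per arm | Fisher | Chi-square |
|---|---|---|
| 16 (one enrolled twice) | 2.05–2.35% | 4.65–5.19% |
| 9 (eight enrolled twice) | 2.6–5.8% | 5.6–10.6% |
| 6 (five three times, one twice) | 3.3–10.4% | 6.8–16.7% |

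Material inflation needs heavy repetition as well as the same-arm rule. Section 9.5.3 expects occlusions to be more likely in younger children, and Phase IIB enrols ages 11 to 17.

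**6. If only first occlusions were analysed** under fresh draws, with repeats filling some of the 34 places, Fisher power is about 74% with 28 children. Type I error is 2.5 to 2.7% (Fisher) and 5.3 to 5.7% (chi-square), slightly above the figures in step 3. This alternative is no better on level and worse on power.

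**The case for a change.** The strongest case for a change is that the intention-to-treat sentence cannot be applied literally to a child in both arms, and that this would be common. Under fresh draws a child enrolled twice lands in both arms with probability 17/33 = 52%. With two such children, the chance that at least one does so is 1 − (2·17·16·15·14 + 2·17·16·17·16)/(34·33·32·31) = 76.4%. An unblinded team could then choose between first, last and all occlusions. If it always took the most favourable, type I error would reach 3.5–3.6% (Fisher) and 7.3–7.5% (chi-square) with 32 children, and 4.5–4.7% and 9.2–9.5% with 28.

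The silence in the text stands, and so do these figures as a worst case. The inference to a needed change does not. Section 6.3.3 defines efficacy over tubes, requires analysis as randomised, and requires deviations and missing responses to be reported under CONSORT. Discarding randomised occlusions would go against that. Fisher's test stays below 5% even in the worst case. It is also the likelier choice: expected failures at 72.5% are 17 × 0.275 = 4.7 per arm, and 17 is exactly the Fisher sample size.

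The remedies that might be offered do not improve on the plan. First occlusions only loses power. Permuting whole children does not fit a design in which one child can hold both allocations. Stating in section 6.4 that the power applies only to 17 distinct children per arm would disagree with step 4.

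**Conclusion.** The plan leaves out a rule for returning Phase IIB children, but analysts would fill the gap sensibly from its own wording: randomise each enrolment, analyse each occlusion in the arm drawn for it, and report how many distinct children lie behind the enrolments. On that reading type I error is 1.8 to 2.1% (Fisher) or 4.4 to 4.7% (chi-square) at a null rate of 72.5%, power is about 81% or 89%, and the planned 17 per arm stands. The same reading serves the secondary endpoints in 6.3.4. Phases I and IIA are descriptive, so no test is affected there.

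This rests on fresh allocation at each enrolment, which the text supports but does not state, and on assumed repeat patterns and correlations. Figures 1 and 8, the flow charts, were not available in the text reviewed and may already show the rule. If returning children were in fact kept in their first arm, step 5 would apply. With one repeat per arm the effect would still be negligible. Writing the rule down would do no harm, but it would not alter the design, the test or the sample size.
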